At the Wihuri Research Institute, a method has been developed to measure LDL particle aggregation propensity (Ruuth *et al.*, 2018). Previous studies demonstrated significant inter-individual variability in LDL aggregation susceptibility, with findings indicating that aggregation-prone LDL predicts future cardiovascular deaths (Ruuth *et al.*, 2018). Our research has also established that the lipid composition of LDL particles regulates their aggregation susceptibility, with LDL particles rich in sphingomyelin being particularly prone to aggregation.

The REDUCE-IT study (Bhatt *et al*, 2019) investigated the effect of eicosapentaenoic acid (EPA; 20:5 n-3) ethyl ester (E-EPA) on blood lipoproteins and cardiovascular disease outcomes. This groundbreaking study demonstrated that a daily dose of 4 g E-EPA significantly reduced cardiovascular events over a 4.9-year follow-up period.

Previous research at Wihuri Research Institute has shown that dietary modifications affecting LDL lipid composition can influence its aggregation propensity (Ruuth *et al.*, 2018). The introduction of plant oils into the diet has been associated with decreased sphingomyelin levels in LDL particles and a significant reduction in aggregation susceptibility. Additionally, intake of alpha-linolenic acid (ALA, 20:3 n-3) (10g/day) or fatty fish (containing approximately 1g of n-3 fatty acids, including

EPA and docosahexaenoic acid (DHA, 22:6 n-3)) led to changes in LDL lipid composition. However, as these modifications were relatively minor, no significant changes in aggregation susceptibility were observed ((Manninen *et al.*, 2018) and unpublished results).

II. OBJECTIVES

This research plan builds upon our previous studies investigating LDL particle modifications in the early stages of atherosclerosis and plaque formation. The primary objective of this study is to determine whether dietary supplementation with E-EPA influences LDL aggregation propensity, particle binding to proteoglycans, or LDL composition. Additionally, plasma or serum samples will be analysed for factors associated with lipid metabolism.

III. STUDY IMPLEMENTATION AND TIMELINE

Study Population

The study aims to recruit 40-70 normolipidemic healthy individuals aged 18-65 years. The study will last for 35 days. The E-EPA-supplementation will last for 28 days, followed by a seven-day washout period. Blood samples are taken before (day 0), during day (day 7), after (day 28) the E-EPA-supplementation and after the washout period (day 35). At day 0 visit, participants will undergo a health examination (inclusive an interview, health questionnaire, anthropometric measurements, blood pressure measurement) and blood withdrawal. The blood will undergo laboratory analyses including complete blood count and key metabolic biomarkers (total cholesterol, LDL cholesterol, HDL cholesterol, triglycerides, apoB-100, apoA-I, and Lp(a), vitamin D3, and blood glucose).

Individuals with exceptionally low LDL aggregation susceptibility will be excluded, as further investigation of their LDL particles would not be meaningful in the present context. Additional exclusion criteria include pregnancy, known blood coagulation disorders, LDL cholesterol >5 mmol/L, triglycerides >3 mmol/L, regular use of anti-inflammatory drugs, and fish allergy.

Supplementation

We will follow the dosing model used in the REDUCE-IT (Bhatt *et al.*, 2019) study, administering 2 grams of pure E-EPA twice daily with meals. Pure E-EPA is not commercially available in Finland, and thus a supplement containing 650 mg of E-EPA and 12.5 μ g of vitamin D3 per capsule will be employed. The supplement will be provided as three capsules to be consumed in the morning and three in the evening, providing a daily total of 3.9 g of E-EPA and 75 μ g of vitamin D3.

Based on previous studies, vitamin D3 is not expected to influence the primary outcome variables. The internationally accepted maximum tolerable daily intake of vitamin D3 for long-term use is 100 μ g. In Finland, the estimated daily dietary intake of vitamin D3 ranges between 10-20 μ g, suggesting that overall vitamin D3-dosage will remain well within safe limits even with the increased intake provided by the supplement. Notably, the participants will be instructed not to use other (commercial) vitamin D supplements during the study.

Research Methods

Blood samples will be analyzed for key parameters related to lipid metabolism and cardiovascular health, including total cholesterol, LDL cholesterol, HDL cholesterol, triglycerides, apoB-100, apoA-I, and Lp(a). Additionally, vitamin D3 and blood glucose levels will be measured. All blood samples will be processed under anonymized identifiers.

Plasma lipoproteins will be isolated via ultracentrifugation. The LDL particle aggregation propensity will be determined using a method developed in our laboratory (Figure 2), employing a dynamic light scattering-based microplate reader (Dyna Pro Plate Reader II). Furthermore, the lipid composition of lipoprotein samples will be analyzed using a method optimized for LDL particle analysis at the University of Helsinki's HiLipid lipidomics unit in collaboration with Associate [name] [name]. The ability of LDL particles to bind to proteoglycans will be assessed by measuring plasma lipoprotein binding to immobilized proteoglycans isolated from the human aorta, a method developed in our laboratory (Ahmed *et al*, 2018).

[figure not shown]

Figure 2. LDL Particle Aggregation Analysis.

LDL is isolated from blood samples using ultracentrifugation. The LDL particles are modified under precisely controlled conditions, with modification induced by enzymatic treatment. This modification leads to strong LDL aggregation, which is monitored by measuring aggregate size using a dynamic light scattering-based method. The method has been developed, optimized, and standardized in our laboratory (Ruuth *et al*, 2018).

Phospholipid transfer protein (PLTP) and cholesterol ester transfer protein (CETP) activities will be assessed using radiometric assays (Groener *et al*, 1986; Jauhainen & Ehnholm, 2005) and Paraoxonase 1 (PON-1) activity by a chromogenic method (Kleemola *et al*, 2002). Lecithin-cholesterol acyltransferase (LCAT) activity will be measured by following formation of radiolabeled cholesterol esters (Jauhainen & Dolphin, 1986).

Angiopoietin-like proteins (ANGPTL) 3, 4, and 8 will be analyzed using specific ELISA assays (Robciuc *et al*, 2010; Tikka *et al*, 2017).

Resolvin levels will be measured in collaboration with the Karolinska Institute in Stockholm. The analysis will be conducted using mass spectrometry optimized for lipid mediators.

Implementation

The responsible physician of the study is [name] (MD, PhD) from the Wihuri Research Institute. Study participants will visit the Wihuri Research Institute, where blood samples will be collected under his supervision. In addition, [name] will personally conduct the baseline health checkups. During these visits, participants will have the opportunity to discuss the study with the physician or the Principal Investigator, [name] [name]. Breakfast will be provided for the participants after each visit.

Blood samples accrued during the study will be processed and analysed at the Wihuri Research Institute, the HiLipid Lipidomics Unit, the Minerva Foundation Institute for Medical Research, and the Karolinska Institutet in Stockholm.

[name], Associate [name] [name], and BSc [name] will inform participants about the study and collect signed consent forms prior to enrollment to the study. Bioanalyst [name] will execute blood withdrawals. BSc [name] will carry out LDL particle isolation, lipidomic analyses, aggregation analyses, and plasma enzyme measurements under the supervision of Associate Professors [name], [name], and [name] and [name] at the Karolinska Institutet. All senior team members will participate in data analysis.

Timeline and Reporting

Participant recruitment will begin once ethical approval and research permits have been granted. Recruitment will be conducted via internal mailing lists at the University of Helsinki and Biomedicum Helsinki. Laboratory analyses will take place between 2019 and 2020, with data analysis and reporting occurring within the same timeframe. The results will be published in international scientific journals, with a target of 1-2 original research articles. Findings will also be presented at international conferences. BSc [name] will include part of the results in his master's thesis. All research team members will contribute to study planning, data evaluation, and reporting.

Funding

The study is funded through research grants to Associate Professors [name] and [name].

Table 1. Cost Estimates

Expenses	Combined
Salaries	
Master's thesis worker's salary – including overheads	15 600 €
Analytics:	
LDL aggregation: 10 €/sample, 200 samples	2 000 €
Lipoprotein isolation: 12.5 €/sample, 200 samples	2 500 €
Lipid extraction and mass spectrometry analyses	5 000 €
Enzymatic analyses	2 000 €
ELISA-analyses	2 500 €

Other costs:	
E-EPA capsules	2 000 €
Breakfast for the participants	500 €
Combined	32 100€

IV. ETHICAL CONSIDERATIONS

The study adheres to Good Clinical Practice (GCP) guidelines, the study plan, and applicable regulations. The study plan aligns with the research objectives and provides sufficient guidance for the research staff to conduct the study appropriately. The research methods used are well-established.

Participants will provide four fasting blood samples over a five-week period. These samples will be analysed for LDL cholesterol, HDL cholesterol, apoB-100, apoA-I, Lp(a), and triglyceride levels. Blood pressure measurements will also be taken during study visits. Participants will receive a summary of these measurements after analyses have been concluded. Prior to each blood sample collection, participants will complete a 24-hour dietary record. As the results related to lipoprotein aggregation and lipidomics remain at an experimental and theoretical level, their clinical significance cannot be assessed at an individual level, and therefore, individual reports on these results will not be provided to participants. However, participants may access study findings after the study has concluded and the results have been published.

E-EPA has not been associated with harmful side effects. Since fish oil-based E-EPA does not contain fish protein, it is generally safe for use; however, due to the high dosage, individuals with fish allergies will not be included in the study. EPA has blood-thinning effects, making anticoagulant medication a contraindication for participation. In the REDUCE-IT trial, 2.3% of E-EPA users reported joint pain, compared to 1% in the placebo group. The amount of vitamin D3 administered in the study exceeds Finland's daily recommended intake but remains well below the EU's upper safe limit of 100 µg, which has been shown to have no adverse effects. Participants taking daily vitamin D3 supplements will be requested to discontinue their use minimum one week prior to commencing the study. Vitamin D3 levels in the blood will be monitored for potential side effects.

Participants may withdraw from the study or revoke their consent at any point prior to its conclusion without any repercussions. Any data collected before consent withdrawal will be used if deemed necessary for the accuracy and reliability of overall study results.

Personal data will be collected in accordance with current data protection regulations. Participants will provide standard personal information, such as name, date of birth, and health-related details, via the consent form. The risk associated with processing this data is assessed as low, and risk assessments will continue throughout the maintenance of the registry. Data protection rights will be upheld during data storage.

Participant samples will be blinded so that only the responsible researcher can link them to personal information. Results or data containing personal identifiers will never be made publicly available. Personal data and study-related documents will be securely stored at the Wihuri Research Institute in locked archive cabinets and password-protected computers. All members of the research team

have been trained in proper data handling. The Principal Investigator will maintain a data registry in compliance with applicable privacy laws.

Participant-specific data will remain confidential and will not be shared with third parties or included in medical records. Sample material containing DNA will not be stored; instead, it will be properly disposed of after sample processing.

V. SCIENTIFIC SIGNIFICANCE

This is an exploratory clinical study utilizing advanced lipid analysis techniques to investigate how E-EPA affects the properties of low-density lipoproteins. Specifically, the study examines changes in LDL lipid composition, its ability to bind to proteoglycans, and its susceptibility to aggregate. Additionally, the study provides insights into how E-EPA influences key plasma enzymes and lipid transfer proteins that regulate lipid metabolism. These findings are significant for assessing the risk of atherosclerosis and coronary artery disease.

VI. REFERENCES

This study is a **single-arm, longitudinal nutritional intervention study with a repeated-measures design**, investigating the effects of icosapent ethyl on blood composition and functional parameters in healthy, normolipidemic volunteers. A total of 38 participants were recruited and screened for inclusion and exclusion criteria based on an initial blood draw. Eligible participants provided a baseline blood sample at Day 0 before receiving the intervention. Participants consumed the supplement daily for four weeks (Days 1–28), with blood samples collected at Days 7 and 28. Following the intervention period, participants underwent a 7-day washout phase, after which a final blood sample was collected at Day 35. No control or placebo group was included in the study, as each participant served as their own control through repeated within-subject comparisons over time.

1. Statistical Methods

The statistical methods employed in this study include tests for normality, group differences, analysis of variance, correlation analysis, time series clustering, principal component analysis (PCA), linear mixed modeling, hierarchical clustering, distance calculations, sparse partial least squares-discriminant analysis (sPLS-DA), uniform manifold approximation projection (UMAP), and machine learning models. Specific methods include:

- **Normality Testing:** D'Agostino-Pearson omnibus K2 test.
- **Group Differences:** Paired multiple t-tests (LIMMA) on log2-transformed data, with false discovery rate (FDR) correction.
- **Analysis of Variance:** One-way ANOVA with post hoc analysis (Benjamini, Krieger, and Yekutieli FDR correction).
- **Correlation Analysis:** Spearman's correlation with exact p-values for small datasets and t-ratio derived p-values for larger datasets.
- **Time Series Clustering:** VSClust fuzzy c-means clustering with k-nearest neighbors (kNN) imputation for missing values.
- **PCA:** Performed on log2-normalized lipid abundances, using centering and scaling.
- **Linear Mixed Modeling:** Implemented using lmer in the lme4 package, with time as a fixed effect and subject as a random effect.
- **Hierarchical Clustering:** Ward's method applied to Euclidean distance matrices from PCA scores.
- **Distance Calculations:** Euclidean distances calculated from PCA scores to assess intra- and inter-subject variability.
- **sPLS-DA:** Conducted via MetaboAnalyst 6.0 with nested cross-validation.
- **UMAP:** Dimensionality reduction using the umap package with predefined parameters.
- **Machine Learning:** XGBoost regression models trained on lipidomic and clinical data using nested cross-validation.

No formal interim analysis was planned.

2. Sample Size and Power Justification

The study initially planned to enrol 40–70 participants, with a total of 72 recruited and 68 enrolled. Due to COVID-19 restrictions, only 38 participants completed the study. A formal power calculation was not conducted, and sample size selection was based on feasibility and the exploratory nature of the study. The final analysis will include only the 38 participants who completed the study.

A sample size assessment was conducted post hoc to evaluate whether the study had sufficient statistical power to detect changes in LDL aggregation, triglycerides, and EPA incorporation. This assessment was based on observed variability in the data and repeated-measures ANOVA. The observed effect size was computed using partial eta-squared ($\eta^2 p$). The effect size was then converted to Cohen's f and used to estimate the required sample size for 80% power. The results indicated that for the primary outcomes, the study had sufficient power to detect moderate-to-large effects, with a required sample size of approximately 16 participants for the observed effect sizes.

3. Level of Significance

A two-tailed significance level of 0.05 was used throughout the study. Multiple hypothesis testing corrections were applied using the false discovery rate (FDR) method where appropriate.

4. Criteria for Termination of the Trial

The trial would be terminated if more than 10% of the participants encountered adverse effects related to the intervention.

5. Handling of Missing Data

A complete case analysis approach was used for analyses requiring full datasets, such as UMAP, PCA, and machine learning analyses. Within these complete cases, missing values were handled using k-nearest neighbors (kNN) imputation where required. However, for single-variable analyses, all available data were used, and missing values were omitted rather than imputed.

6. Deviations from the Original Statistical Plan

The study deviated from the original protocol in the following ways:

- **Sample Size Reduction:** The original plan aimed for 40–70 participants, but only 38 completed the study due to COVID-19 restrictions. The final analysis includes only these 38 participants under a per-protocol approach rather than an intention-to-treat model.
- **Changes in Outcome Assessments:** Some planned secondary outcomes, including enzyme activity assays (PLTP, CETP, PON-1, LCAT) and ELISA assays for ANGPTLs and resolvins, were not conducted due to COVID-19-related constraints.
- **Changes in study collaborators:** Due to Covid-19 travel restrictions and delays, the international collaboration with Karolinska Institute was halted and [name] [name] and PhD [name] removed from the research team.

- **Expanded Statistical Methods:** The study incorporated additional statistical methods, including machine learning (XGBoost), time series clustering (VSClust), hierarchical clustering, UMAP, and sPLS-DA, which were not in the original protocol.
- **Data Handling Approach:** The original plan allowed for analysis of partially completed cases, but the final study adopted a complete case analysis approach, excluding participants with missing time points.
- **Stopping Criteria Introduced:** The original plan did not specify stopping rules. The final study introduced a stopping rule stating that if >10% of participants experienced adverse effects, the study would be terminated.

These modifications were made to accommodate study constraints while maintaining scientific rigor.

7. Selection of Subjects for Analysis

The final analysis will include only the 38 participants who completed the study, following a per-protocol approach. Participants with missing time points will not be included in the analysis.

8. Direct Access to Source Data/Documents

The study sponsor will ensure that the investigator(s)/institution(s) permit trial-related monitoring, audits, IRB/IEC review, and regulatory inspection(s), providing direct access to source data/documents. The source data will not be made publicly available in any repository due to legislation on anonymity. Data is stored on secure backup media and deposited on a secure university server for long-term storage and controlled access.

9. Quality Control and Quality Assurance

The study adhered to standardized protocols for data collection, processing, and statistical analysis to ensure data integrity and reliability. Quality control measures were implemented to maintain consistency and accuracy in data handling.

10. Ethical Considerations

Written informed consent was obtained from all participants. The study adhered to the ethical guidelines of the Declaration of Helsinki and was approved by an appropriate ethics committee.

11. Data Handling and Record Keeping

All study data were securely stored in a regulatory-compliant manner, with participant identifiers removed to maintain confidentiality. Data processing was performed using GraphPad Prism v10.1.2 and RStudio (Version 2023.12.1, build 402, Posit Software, PBC).

12. Financing and Insurance

The study is sponsored by the Wihuri Research Institute, a private, foundation-funded academic institution. Wihuri Research Institute is supported by the Jenny and Antti Wihuri Foundation. Additional funding for this study was received through grants from private foundations and the Research Council of Finland. Funding for this study was solely for academic research, with no commercial interests involved. All study participants were insured by the Wihuri Research Institute.

13. Publication Policy

The publication policy follows the predefined guidelines agreed upon by study investigators. The study findings will be published in gold/green open-access peer-reviewed journals, ensuring transparency and reproducibility.

14. Supplements

Further details regarding statistical methodologies, exploratory analyses, and supplementary findings can be found in the Supplementary Methods section of the final study report.

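### SAP section 1 lists a one-way ANOVA with no within-subject term or sphericity handling for a four-visit single-arm design; the repeated-measures test, its correction and its outcomes should be named

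*Combined protocol and SAP*

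**What the plan says.** The SAP's opening paragraph describes a single-arm study in which "each participant served as their own control through repeated within-subject comparisons over time". After the Day 0 baseline the participants took the supplement, "with blood samples collected at Days 7 and 28", and a washout followed, "after which a final blood sample was collected at Day 35". That makes four visits, separated by 7, 21 and 7 days.

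Section 1 (Statistical Methods) gives the analysis of variance in one line: "One-way ANOVA with post hoc analysis (Benjamini, Krieger, and Yekutieli FDR correction". The same list contains two methods that respect the pairing: paired LIMMA t-tests on log2 data, and an lmer model "with time as a fixed effect and subject as a random effect". None of the three is tied to a named outcome.

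Section 2 (Sample Size and Power Justification) states: "A formal power calculation was not conducted, and sample size selection was based on feasibility and the exploratory nature of the study". It then reports a post hoc assessment for LDL aggregation, triglycerides and EPA incorporation. "This assessment was based on observed variability in the data and repeated-measures ANOVA", it says, "with a required sample size of approximately 16 participants for the observed effect sizes".

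Section 11 names the software but not the options used. Sphericity is not mentioned anywhere. Section 14 refers the reader to Supplementary Methods in the final report for further methodological detail; that text is not part of the documents reviewed.

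**The concern.** The ANOVA line and the post hoc assessment carry different labels, and the labels can mean different tests. An ordinary one-way ANOVA on four visits treats the 4 × 38 = 152 values as independent, so stable differences between people stay in the error term. A repeated-measures ANOVA removes them. If the line were followed as written, a real change in LDL aggregation could be missed, and the figure of about 16 participants would describe a different test.

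If the line is shorthand for one within-subject factor, the risk runs the other way. The uncorrected repeated-measures F test, and post hoc contrasts using its pooled error, assume that all visit differences have the same variance. With gaps of 7, 21 and 7 days that may fail, and the false-positive rate then exceeds 5%.

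Under either reading, the SAP does not tell the reader which method produced the p-value for LDL aggregation.

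**Working it through.** **Inputs from the SAP:** k = 4 visits (opening paragraph), N = 38 (section 2), two-tailed alpha 0.05 (section 3), 80% power and about 16 participants by repeated-measures ANOVA (section 2). The SAP gives no partial eta-squared, Cohen's f, SD or correlation. Every correlation below is assumed and shown as a range.

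**1. The plan's own figure.** With no effect size reported, 16 can only be back-solved. For F(3, 45), where 45 = 3 × 15, 80% power needs a noncentrality of 11.90, or 11.90/16 = 0.743 per participant. The implied effect depends on the convention:
- f² = 11.90/(15 × 3) = 0.264, so partial eta-squared = 0.264/1.264 = 0.209;
- f² = 11.90 × (1 − 0.5)/(16 × 4) = 0.093, so partial eta-squared = 0.093/1.093 = 0.085.

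So 16 is attainable but cannot be verified.

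**2. Literal reading (independent groups).** With equal correlation rho between visits, the SE of a visit difference is overstated by 1/√(1 − rho). The test is referred to F(3, 148), where 148 = 4 × 37. Its numerator is (1 − rho)·χ²(3, λ)/3 and its denominator is [(1 + 3rho)·χ²(37) + (1 − rho)·χ²(111)]/148. At the effect needing 16, λ = 0.743 × 38 = 28.25. Repeated-measures F(3, 111) then has 99.6% power.

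| Assumed rho | SE overstated by | Actual type I error | Power at N = 38 |
|---|---|---|---|
| 0.3 | 1.20 | 1.2% | 98% |
| 0.5 | 1.41 | 0.2% | 93% |
| 0.7 | 1.83 | 0.005% | 63% |
| 0.8 | 2.24 | <0.001% | 25% |

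The power loss is small at rho of 0.5 or below and large above it. If partial eta-squared of 0.085 were instead the observed within-subject value, power at N = 38 would be 76% for repeated measures and 56%, 32%, 6% and 1% for the literal test.

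**3. Repeated-measures reading without correction.** Type I error was simulated at N = 38. For decay with time, the correlation is r^(days/7). With r = 0.9, for example, Days 0 and 7 correlate 0.90, Days 0 and 28 correlate 0.9⁴ = 0.66, and Days 0 and 35 correlate 0.9⁵ = 0.59. The contrast is tested before FDR adjustment.

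| Correlation between visits (assumed) | Overall F | Day 28 minus Day 0, pooled error |
|---|---|---|
| Equal at all visits | about 5% | about 5% |
| Pure decay, r from 0.7 to 0.95 | about 7% to 8% | about 8% to 9% |
| Decay, 10% of variance independent noise | about 6% to 7% | about 7% to 8% |
| Decay, 50% independent noise | about 5% | about 6% |

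Under pure decay, the Geisser-Greenhouse correction and a paired SE each bring the rate back to about 5%.

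**4. Cost of correcting when it is not needed.** Take equal correlation, an effect with 80% repeated-measures power at N = 38 (noncentrality 11.29), and visit means in the pattern 0, 0.5, 1, 0.5. Geisser-Greenhouse lowers overall power from 80% to 79%. The paired SE lowers power for Day 28 minus Day 0 from 91.5% to 90.6%.

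**The case against.** The best defence is that one-way can properly mean one within-subject factor. Time is the only factor, the design is described as within-subject, and section 2 uses the repeated-measures form. That stands: it is the likelier reading, and the low power figures then do not apply. A reader might infer that an independent-groups ANOVA was actually run. The SAP does not show that, because it neither states nor rules out matching of visits.

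A reader might also infer that the study was sized for one test and analysed by another. The documents do not support this either. Recruitment was set by feasibility, and repeated-measures ANOVA underlies only the post hoc assessment.

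Nor does the method list ignore pairing, since the LIMMA tests and the lmer model both respect it. What remains open is which of the three methods applies to which outcome.

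The 8% and 9% rates sit at the unfavourable end. They assume correlation that decays purely with time, and modest independent assay or visit noise brings them down. The study is exploratory, and section 14 may lead to text that settles the question. Even so, the test of the primary outcomes belongs in the SAP itself, and the SAP's silence on sphericity is a fact under either reading.

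**Conclusion.** The point holds as an under-specification that should be corrected; it is not a proven contradiction or a demonstrated analysis error. Following the written line literally would use the wrong error term and make the test conservative, with a loss that ranges from trivial to severe as within-person correlation rises. Under the likelier repeated-measures reading, the exposure is a modest excess of false positives: none if visits are equally correlated, and up to about 3 percentage points overall (8% against 5%) and 4 for a pooled-error contrast (9% against 5%) under pure time decay. All sizes rest on assumed correlations, and the literal power range also rests on the back-solved effect behind 16. Confidence is medium, because the options actually used and the Supplementary Methods cannot be seen.

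**What to change.** Replace the ANOVA line in section 1 with: *One-way repeated-measures ANOVA (visit as within-subject factor, four levels) with Geisser-Greenhouse correction, and paired post hoc comparisons each with its own paired SE, followed by the stated FDR correction.*

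In addition:
- State which outcomes use this test, which use LIMMA and which use lmer, starting with LDL aggregation, triglycerides and EPA incorporation.
- If a mixed model is used where a visit value is missing, give it an unstructured visit covariance. A random intercept alone assumes equal correlation between visits; on complete data with a non-negative subject variance, its visit test is the uncorrected F test again.
- Disclose that this specification was written after data collection.

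The cost is SAP wording and a re-run on data already held, with about one point of power lost if visits are in fact equally correlated. If a corrected repeated-measures ANOVA was already run, only the wording changes.
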